9.7.3 Electrocardiogram

The raw values and change from baseline values will be summarized at each scheduled visit for Safety Set during 110 TE Period: PR, QT, and QTc for HR interval (QTcF), QRS duration, and HR. The number and percentage of subjects with at least 1 threshold analysis event during the entire 110 TE Period will be summarized by treatment group. The threshold analysis criteria are listed in [Section 11.3](#).

9.7.4 Vital Signs

The raw values and change from baseline values will be summarized at each scheduled visit for Safety Set during 110 TE Period: systolic and diastolic blood pressure (mm Hg), body temperature (°C), HR (beats per minute [bpm]), and respiratory rate (breaths per minute). The number and percentage of subjects with at least 1 threshold analysis event during the entire 110 TE Period will be summarized. The threshold analysis criteria are provided in [Section 11.3](#).

9.7.5 Pulse Oximetry

The raw values and change from baseline values will be summarized at each scheduled visit for Safety Set during 110 TE Period for the percent of oxygen saturation by pulse oximetry. The number and percentage of subjects with shift changes from baseline (normal/missing and low according to the reference range) to the lowest percent of oxygen saturation during the entire 110 TE Period will be tabulated.

9.7.6 Ophthalmologic Examination

The ophthalmologic examination results may be listed for subjects < 18 years old (age on the date of informed consent/assent in the parent study) with cataracts anytime during 110 TE Period.

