Weight and height ^j		X		X	X	X	X	X	X
Ophthalmological history ^k		Day 1							
Ophthalmologic examination ^l	X ^{h,m}	X ⁿ			X		X	X ^o	X ^p
Complete physical examination ^p		X			X		X	X	
Pregnancy test ^q		urine		urine	urine	urine	serum	serum	serum

^h If the baseline ophthalmologic examination (see Footnote **m**) is not conducted as a parent study assessment but is conducted during the Day -28 to Day -1 period of Study VX14-661-110, informed consent/assent will be obtained before this examination and will not be obtained again on Day 1 of Study VX14-661-110.

ⁱ Questionnaires must be completed before the start of any other assessments scheduled at that visit (**Section 11.1**). The CFQ-R must be completed first.

^j Weight and height will be measured before dosing with shoes off (**Section 11.7.2**). Height will be collected only for subjects ≤21 years of age (age on the date of informed consent/assent in the parent study).

^k Required on Day 1 for all subjects without a documented ophthalmological history from the parent study. Not required at the Returning Visit.

^l Ophthalmologic examinations will be conducted on subjects < 18 years of age (age on the date of informed consent/assent in the parent study) by a licensed ophthalmologist.

^m An ophthalmologic examination will be conducted on subjects < 18 years of age (age on the date of informed consent/assent in the parent study) by a licensed ophthalmologist within 28 days before enrollment on Day 1 (**Section 11.8.7**). This examination may be conducted while the subject is participating in the parent study. If this examination is not conducted during the Day -28 to Day -1 period, subjects are required to complete the Day 1 ophthalmologic examination.

ⁿ The Day 1 ophthalmologic examination is not required for subjects who complete the baseline ophthalmologic examination during the Day -28 to Day -1 period (this examination may be conducted while the subject is participating in the parent study).

^o Subjects <18 years of age (age on the date of informed consent/assent in the parent study) who discontinue treatment after receiving at least 1 dose of study drug will have an ophthalmologic examination conducted by a licensed ophthalmologist (**Section 8.1.1.3**). The examination may be completed at either the ETT or Safety Follow-Up Visit, but must be completed by the date of the Safety Follow-Up Visit.

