12.3.5.7 Ophthalmologic Examination

Ophthalmologic examination results will be listed for subjects < 18 years old (age on the date of informed consent/assent in the parent study) with cataracts anytime during the TE period.

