5 STUDY ENDPOINTS

5.1 Primary Endpoints

Part A

Treatment Cohort

Safety and tolerability of long-term treatment of VX-661/IVA based on adverse events (AEs), ophthalmologic exams (subjects <18 years of age [age on the date of informed consent/assent in the parent study]), clinical laboratory values (serum chemistry, hematology, coagulation, lipids, vitamins, and urinalysis), standard digital electrocardiograms (ECGs), vital signs, and pulse oximetry.

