9.7 Safety Analysis

9.7.1 Adverse Events

For each individual parent study, summary table of treatment emergent AEs during the respective parent study will be included in the Study 110 CSR. The parent studies are 103, 111, 106, 108, 107 and 109.

The analysis of Adverse Events in the rest of section 9.7.1 will be based on the Safety Set during **110 TE Period.**

For analysis purposes, AEs will be categorized as pre-treatment AEs, treatment-emergent adverse events (TEAEs), or post-treatment AEs:

- **Pretreatment AE:** any AE that started before the first dose of study drug in Part A.
- **TEAE:** any AE that increased in severity or that was newly developed at or after the first dose of study drug in Study Part A through the end of 110 TE Period.
- **Post-treatment AE:** any AE that increased in severity or that was newly developed after 110 TE Period.

For AEs with missing or partial start date, if there is no clear evidence that the AEs started (or increased in severity) before the first dose, the start date will be imputed to the first dosing date and the AE will be considered as TEAE. As an intermediate step for programming purposes, imputation rules for missing or partially missing AE start/end dates are defined in [Section 11.4](#).

TEAEs will be classified into 4 categories of relationship to the study drugs: not related, unlikely related, possibly related, related.

TEAEs will be classified into 4 categories of severity:

- **Mild (Grade 1):** Mild level of discomfort and does not interfere with regular activities
- **Moderate (Grade 2):** Moderate level of discomfort and significantly interferes with regular activities
- **Severe (Grade 3):** Significant level of discomfort and prevents regular activities
- **Life-threatening (Grade 4 and 5):** Any adverse drug experience that places the subject, in the view of the investigator, at immediate risk of death.

All the summary tables of TEAEs display counts and exposure-adjusted event rates for the Safety Set in Study 110.

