9.7.1.2 TEAEs, Related TEAEs, Serious TEAEs, Related Serious TEAEs, Grade 3/4 TEAEs

Using MedDRA System Organ Class (SOC) and Preferred Term (PT), the number of subjects and exposure-adjusted event rates for the following TEAEs are summarized based on the Safety Set during 110 TE Period:

- TEAEs by PT and by SOC/PT

- Related TEAEs by SOC/PT
- Serious TEAEs by PT and by SOC/PT
- Related serious TEAEs by SOC/PT
- Grade 3/4 TEAEs by SOC/PT

Multiple occurrences of the same adverse event or a continuing adverse event for the same subject will be counted once. Related adverse events include related, possibly related, and missing categories. The summary tables will be presented in descending order of frequencies in the column based on Safety Set in Study 110.

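### Eye examination in subjects under 18 is a named primary safety component, but the only visible planned output is an optional listing of cataract cases, with no number examined and no count of new findings

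*SAP*

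**What the plan says.** SAP 5.1 defines the primary endpoint as safety and tolerability "based on adverse events (AEs), ophthalmologic exams (subjects <18 years of age", followed by laboratory values, ECGs, vital signs and pulse oximetry. Protocol 7.1 has the same list.

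On who is examined, Protocol Table 3-1 states that "Ophthalmologic examinations will be conducted on subjects < 18 years of age", with age taken at consent or assent in the parent study. Examinations are scheduled at baseline (Day -28 to Day -1, or Day 1), Week 48, Week 96, and at the Early Treatment Termination (ETT) or Safety Follow-up Visit after early discontinuation.

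On analysis, Protocol 12.3.5.7 says "Ophthalmologic examination results will be listed for subjects < 18 years old" if they had cataracts during the treatment-emergent period. SAP 9.7.6 says "The ophthalmologic examination results may be listed for subjects < 18 years old", restricted to those "with cataracts anytime during 110 TE Period". These are the only visible analysis statements for the examination.

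The adverse event tables include "TEAEs by PT and by SOC/PT" (SAP 9.7.1.2). On their population, SAP 9.7.1 says: "All the summary tables of TEAEs display counts and exposure-adjusted event rates for the Safety Set in Study 110".

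**The concern.** A listing restricted to cases has no denominator. Examined subjects with clear lenses never appear in it, so an empty listing looks the same whether many adolescents were examined and found clear or few were examined at all. The rule also selects any cataract during the Study 110 treatment-emergent period. It therefore does not separate a cataract that developed on treatment from one already present at entry. Protocol 11.8.7 lets subjects with a clinically significant baseline cataract or lens opacity enrol, so the distinction matters. It names cataracts only, whereas Protocol 10.6 and 11.8.7 act on a cataract or a lens opacity.

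The SAP's change from *will* to *may* makes even this listing optional, and no reason is given. What is at stake is whether the study report can say how many treated adolescents were examined, how many had a new lens finding, and how precisely that is known.

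**Working it through.** The plan states no figure for this endpoint, so there is none to reproduce. The check compares the planned outputs and then illustrates the value of a denominator.

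**1. Output planned for each primary component (SAP 9.7)**

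| Component | Visible planned output |
|---|---|
| Adverse events | Counts and exposure-adjusted event rates |
| Chemistry, hematology, coagulation, lipids, vitamins | Values by visit, shifts, number and % meeting threshold criteria |
| Urinalysis | Listing of abnormal results |
| ECG, vital signs | Values by visit, number and % with a threshold event |
| Pulse oximetry | Values by visit, number and % with shifts |
| Eye examination (<18) | Optional listing of cataract cases |

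SAP Table 11-1 assigns visit windows to ECG, vital signs, oximetry and laboratory tests, but not to eye examinations. Protocol 12.3.5 omits eye examinations from its list of safety endpoints to be assessed.

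**2. Whether the adverse event tables supply the count.** A cataract reported as an adverse event would appear by preferred term. The exposure behind the rate comes from the whole Safety Set, including adults with no scheduled lens examination. SAP 9.7.1.4 defines special groupings for transaminase and respiratory terms, not for lens findings. Capture is also uncertain. Protocol 11.8.2, 11.8.3 and 11.8.4 each direct that clinically significant abnormalities be recorded as adverse events, while 11.8.7 has no such instruction. Protocol 13.1.1.2 gives a general rule whose examples omit eye examinations, though its list is not exhaustive.

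**3. Whether enrolment can stand in for the number examined.** The Treatment Cohort is 23 + 464 + 159 + 227 + 138 + 33 = 1,044 (SAP 6.2). Subjects from Studies 107 and 109 were discontinued early (SAP 7.1): 159 + 138 = 297, and 297/1,044 = 28%. The number with a Week 48 or Week 96 examination may therefore be well below the number enrolled, and no visible output reports it.

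**4. What a zero count would mean.** The number under 18 is not given. Assume 15% to 30% of 1,044: 0.15 × 1,044 = 157 and 0.30 × 1,044 = 313. With zero events among n examined, the exact two-sided 95% upper limit is 1 − 0.025^(1/n):

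- n = 313: about 1.2%
- n = 157: about 2.3%
- n = 100 (assumed, if fewer have a post-baseline examination): 3.6%

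The rule of three (3/157 = 1.9%, 3/313 = 0.96%) approximates a one-sided 95% bound, so it should not be read as the limit of a two-sided interval.

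**5. Which baseline.** The Study 110 eye examination falls within 28 days before Day 1, or on Day 1 (Table 3-1; Protocol 11.8.7). The SAP 9.1 safety baseline is the last assessment before the first active dose, which may lie in the parent study. For a subject already treated there, the two differ: a lens finding that arose on parent-study treatment would count as baseline under the first and as new under the second.

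**The case against.** The endpoint is broad: safety and tolerability judged from several sources. Neither document names a rate of new lens opacities as the quantity to estimate. Listing alone is also how both documents handle urinalysis, another component of the same endpoint. The SAP largely follows the protocol here; only the modal verb has changed. Clinically significant cataracts can reach the adverse event tables and the listing of all adverse events by subject, and Protocol 12.3.3 mentions listing all subject data, although under background characteristics. Finally, an entry in the SAP contents just before 9.7.2, and another after Appendix 11.4, are redacted.

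Much of this stands. A reader might infer that no cataract count will be reported at all, or that the plan cannot address its primary endpoint. The documents do not support either reading. There is a partial route through adverse events, the redacted entries cannot be counted as missing, and the supportable statement is only that no incidence among examined subjects is planned in the visible text. A reader might also infer that the adverse event tables understate incidence by a fixed factor, such as 1,044 divided by the number under 18. That does not follow either. The SAP plans counts and exposure-adjusted rates, so dilution depends on shares of follow-up time, which are unknown, and the share under 18 is itself an assumption.

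The urinalysis parallel is weaker than it looks. Urinalysis is scheduled for every subject at nearly every visit, so its denominator is close to the Safety Set. Eye examinations are scheduled for a subset of unstated size at a few time points.

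**Conclusion.** The point holds as a gap in planned output plus a discrepancy between the documents. The SAP makes optional a listing that the protocol makes mandatory. Nothing visible plans the number examined, baseline lens status or the number with new findings for a named primary safety component. As written, the output cannot give incidence among examined subjects, separate new from existing cataracts, or put a bound on a zero count.

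The size cannot be fixed from the documents. The upper limits of about 2.3% and 1.2% rest on assumed numbers examined (157 and 313) and on zero events; they show only that the missing denominator changes what a zero means. The conclusion does not depend on those figures. This is a worthwhile, inexpensive correction to make before data lock. It does not invalidate the other safety analyses.

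**What to change.** 1. In SAP 9.7.6, change *may* to *will*, matching Protocol 12.3.5.7.
2. Add one descriptive table for Safety Set subjects under 18 (age at parent-study consent or assent) showing:
   - the number with a baseline and at least one post-baseline eye examination;
   - the number with a cataract or lens opacity at baseline;
   - among those clear at baseline, n (%) with a new finding overall and at Week 48, Week 96 and ETT/Safety Follow-up, with an exact two-sided 95% CI.
3. State the baseline: the Study 110 eye examination (within 28 days before Day 1, or on Day 1). Split the table by whether the subject had active treatment in the parent study, because findings that arose on that treatment would otherwise count as baseline. For Study 108 rollovers, say whether active treatment in either period counts.
4. State that nominal visits are used, or add eye examinations to the visit windows.

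The examinations are already scheduled, so no new visit or data collection is needed. The cost is one extra table and an explicit baseline choice. With the Study 110 baseline, the table describes new findings during Study 110 only; the split makes that limit visible but does not recover findings from the parent study.

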9.7.7 Pregnancy Tests

Positive urine and serum pregnancy test results during baseline and TE period will be listed.

11 APPENDICES

11.1 Analysis Visit Window Mapping Rules

Table 11-1 Visit Window Mapping Rules for Safety Measurements

Assessments	Visit	Target Study Day	Visit Window (in study days)

 • Standard 12-lead ECG • Vital signs • Pulse oximetry • Labs 
 ○ Chemistry ○ Hematology 	Day 1	1	[1, 1]
	Day 15	15	[2, 36]
	Week 8	57	[37, 85]
	Week 16	113	[86, 141]
	Week 24	169	[142, 211]
	Week 36	253	[212, 295]
	Week 48	337	[296, 379]
	Week 60	421	[380, 463]
	Week 72	505	[464, 547]
	Week 84	589	[548, 631]
	Week 96	673	[632, 687]
	ETT	N/A	Follow the individual visit window to be mapped to individual visits
Safety Follow-up Visit	N/A	Nominal (remain as SFU)	

 • Coagulation • Lipid Panel • Labs 
 ○ Vitamin Level ○ Urinalysis 	Day 1	1	[1, 1]
	Week 8	57	[2, 85]
	Week 16	113	[86, 141]
	Week 24	169	[142, 211]
	Week 36	253	[212, 295]
	Week 48	337	[296, 379]
	Week 60	421	[380, 463]
	Week 72	505	[464, 547]
	Week 84	589	[548, 631]
	Week 96	673	[632, 687]
	ETT	N/A	Follow the individual visit window to be mapped to individual visits
	Safety Follow-up Visit	N/A	Nominal (remain as SFU)

Note: spirometry assessments, BMI, weight, and height will be used for both efficacy and safety purposes. Their measurements will follow the visit windowing rules for efficacy measurements.

Table 11-2 Visit Window Mapping Rules for Efficacy Measurements

Assessments	Visit	Analysis Visit	Target Study Day	Visit Window (in study days)

 • Spirometry • CFQ-R 	Day 15	Study 110 Day 15	15	[2, 36]
	Week 8	Study 110 Week 8	57	[37, 85]
	Week 16	Study 110 Week 16	113	[86, 141]
	Week 24	Study 110 Week 24	169	[142, 211]
	Week 36	Study 110 Week 36	253	[212, 295]
	Week 48	Study 110 Week 48	337	[296, 379]
	Week 60	Study 110 Week 60	421	[380, 463]
	Week 72	Study 110 Week 72	505	[464, 547]
	Week 84	Study 110 Week 84	589	[548, 631]
	Week 96	Study 110 Week 96	673	[632, 687]
	ETT		N/A	Follow the individual visit window to be mapped to individual visits
Safety Follow-up Visit	Safety Follow-up Visit	N/A	Follow the individual visit window to be mapped to individual visits if fall within the upper boundary of the window for the last scheduled visit (Day 687); or remain as SFU if otherwise.	

 • Weight and height • BMI 	Week 8	Study 110 Week 8	57	[2, 85]
	Week 16	Study 110 Week 16	113	[86, 141]
	Week 24	Study 110 Week 24	169	[142, 211]
	Week 36	Study 110 Week 36	253	[212, 295]
	Week 48	Study 110 Week 48	337	[296, 379]
	Week 60	Study 110 Week 60	421	[380, 463]
	Week 72	Study 110 Week 72	505	[464, 547]
	Week 84	Study 110 Week 84	589	[548, 631]
	Week 96	Study 110 Week 96	673	[632, 687]
	ETT	ETT	N/A	Follow the individual visit window to be mapped to individual visits
	Safety Follow-up Visit	Safety Follow-up Visit	N/A	Follow the individual visit window to be mapped to individual visits if fall within the upper boundary of the window for the last scheduled visit (Day 687); or remain as SFU if otherwise.

Note:

1. To apply the above visit windows, please first label Day 1 for the date of the first dose in Study 110 drug, and use the nominal visit names to label SFU (for safety).
2. After the SFU (for safety) measurements are determined; the above visit windows will be applied to determine the analysis visit names for all remaining measures at scheduled or unscheduled visits.
3. For all efficacy parameters, if there are multiple measurements within a visit window, the record at the scheduled visit will be used. Otherwise,
 - If there are no measurements at the scheduled visit, then the record closest to the target day will be used;
 - If there are multiple records with the same distance to the target day, the latest record will be used.
 - Assessments at the early treatment termination (ETT) visit will follow the windowing rules for regular visits.
 - Assessments at safety follow-up (SFU) visit will follow the windowing rules for regular visits if they fall within the upper boundary of the window for the last scheduled visit; it will remain as the SFU if it goes beyond the upper boundary of the window for the last scheduled visit.
4. For all safety parameters, if there are multiple measurements within a visit window, then 1) the record closest to the target day will be used, with the exception of the threshold analysis in which the worst record will be used; 2) if there are multiple records within the same distance of the target day, the latest record will be used; or 3) the SFU visit will not be windowed; instead, the nominal visit will be used in relevant analysis.

Special handling for ECG:

- On Day 1 & Day 15, ECGs will be collected before dosing and at 1.5 and 4 hours after the morning dose. None of the measures on Day 1 or Day 15 will be mapped into other visits.
 - Day 1 post-dose and Day 15 pre-/post-dose measurements will be analyzed based on nominal visit names.
 - On Day 1, the pre-dose measurements will be performed in triplicate, the average of the triplicate will be used as pre-dose measurement on Day 1. Only pre-dose measurement with nominal visit names related to the triplicate shall be used in this average.
- The visit window in the above table will still apply for the ECG data after Day 15.

11.2 Coefficients for Hankinson and Wang Methods for Calculating Predicted Spirometry Parameters

Percent predicted FEV₁ is the ratio of FEV₁ (L) to the predicted FEV₁ (L), expressed as a percentage. The predicted FEV₁ (L) will be calculated using the Hankinson¹ and Wang² standards.

The Hankinson standard will be applied to male subjects 18 years and older and female subjects 16 years and older; the Wang standard will be applied to male subjects 6 to 17 years and female subjects 6 to 15 years of age. During the study, the subjects who have a birthday that would move them from Wang to Hankinson will use the Wang standard before that birthday and the Hankinson standard at or after that birthday.

Hankinson Normal Values (HNVs) will be calculated for FEV₁, forced vital capacity (FVC), forced expiratory flow mid expiratory phase (FEF_{25-75%}), and FEV₁/FVC% using the Hankinson equation:

$$\text{Predicted lung function parameter} = b_0 + b_1 \times \text{age} + b_2 \times \text{age}^2 + b_3 \times \text{height}^2$$

In the equation, height is given in centimeters, age is given in years, and the coefficients b₀, b₁, b₂, and b₃ are determined based on subject's sex, race, and age group as provided in [1].

Wang Normal Values (WNVs) will be calculated for FEV₁, FVC, FEF_{25-75%}, and FEV₁/FVC using the Wang equation:

$$\ln(\text{Predicted lung function parameter}) = \alpha + \beta \ln(\text{height})$$

Wang Normal Values (WNVs) will be calculated for FEV₁, FVC, FEF_{25-75%}, and FEV₁/FVC using the Wang equation. In the equation, height is given in meters, and the coefficients α and β are determined based on subject's sex, race, and age as provided in [2].

If either height or age is missing, and the spirometry measurement is non-missing, the last non-missing value of height and age will be used in the calculation of predicted values.

11.3 Threshold Analysis Criteria

Table 11-3 Threshold Criteria for Clinical Chemistry and Hematology

Parameter	Threshold Criteria
Clinical Chemistry	
CPK	>ULN - ≤ 2.5 x ULN >2.5 - ≤ 5 x ULN >5 - ≤ 10x ULN >10 x ULN
Creatinine	>ULN - ≤ 1.5 x ULN >1.5 - ≤ 3.0 x ULN >3.0 - ≤ 6.0 x ULN >6.0 x ULN
Blood Urea Nitrogen	>ULN - ≤ 1.5 x ULN >1.5 - ≤ 3.0 x ULN >3.0 - ≤ 6.0 x ULN >6.0 x ULN
Sodium	Hyponatremia <LLN - ≥130 mmol/L <130 – ≥120 mmol/L <120 mmol/L Hypernatremia >ULN - ≤ 150 mmol/L >150 mmol/L- ≤155 mmol/L >155 mmol/L - ≤ 160 mmol/L >160 mmol/L
Potassium	Hypokalemia <LLN – ≥ 3.0 mmol/L <3.0 – ≥ 2.5 mmol/L <2.5 mmol/L Hyperkalemia >ULN – ≤ 5.5 mmol/L >5.5 – ≤ 6.0 mmol/L >6.0 – ≤ 7.0 mmol/L >7.0 mmol/L
Total Cholesterol	>ULN – ≤ 7.75 mmol/L >7.75 – ≤ 10.34 mmol/L >10.34 – ≤ 12.92 mmol/L >12.92 mmol/L

Triglycerides	>1.71 – ≤ 3.42 mmol/L >3.42 – ≤ 5.7 mmol/L >5.7 – ≤ 11.4 mmol/L >11.4 mmol/L
Glucose	Hypoglycemia <3.0 – ≥ 2.2 mmol/L <2.2 – ≥ 1.7 mmol/L <1.7 mmol/L Hyperglycemia >ULN - ≤ 8.9 mmol/L >8.9 – ≤ 13.9 mmol/L >13.9 – ≤ 27.8 mmol/L >27.8 mmol/L
Albumin	<35 - ≥ 30 g/L <30 – ≥ 20 g/L <20 g/L
Amylase	>ULN - ≤ 1.5 x ULN >1.5 – ≤ 2.0 x ULN >2.0 – ≤ 5.0 x ULN >5.0 x ULN
Lipase	>ULN - ≤ 1.5 x ULN >1.5 – ≤ 2.0 x ULN >2.0 – ≤ 5.0 x ULN >5.0 x ULN
Direct bilirubin	>ULN - ≤ 1.5 x ULN >1.5 – ≤ 2 x ULN >2 – ≤ 3 x ULN >3 – ≤ 10 x ULN >10 x ULN
GGT	>ULN - ≤ 2.5 x ULN >2.5 – ≤ 5.0 x ULN >5.0 – ≤ 20.0 x ULN >20.0 x ULN
Calcium	Hypercalcemia >ULN - ≤ 2.9 mmol/L >2.9 – ≤ 3.1 mmol/L >3.1 – ≤ 3.4 mmol/L >3.4 mmol/L Hypocalcemia <LLN - ≥ 2.0 mmol/L

	
<2.0 – ≥1.75 mmol/L <1.75 – ≥ 1.5 mmol/L <1.5 mmol/L

Magnesium	
Hypermagnesemia >ULN - ≤ 1.23 mmol/L >1.23 – ≤ 3.30 mmol/L >3.30 mmol/L
 <hr/> 
Hypomagnesemia <LLN - ≥ 0.5 mmol/L <0.5 – ≥ 0.4 mmol/L <0.4 – ≥ 0.3 mmol/L <0.3 mmol/L

Inorganic phosphate	
Hypophosphatemia <0.74 – ≥ 0.6mmol/L <0.6 – ≥ 0.3 mmol/L <0.3 mmol/L

ALT	
>ULN - ≤ 3 xULN >3 – ≤ 5 xULN >5 – ≤ 8 xULN >8 – ≤ 20.0 xULN >20.0 x ULN

AST	
>ULN - ≤ 3 xULN >3 – ≤ 5 xULN >5 – ≤ 8 xULN >8 – ≤ 20.0 xULN >20.0 x ULN

ALT or AST	
(ALT>ULN and ALT ≤ 3 xULN) or (AST>ULN and AST≤ 3 xULN); (ALT>3 xULN and ALT ≤ 5 xULN) or (AST>3xULN and AST≤ 5 xULN); (ALT>5 xULN and ALT ≤ 8 xULN) or (AST>5xULN and AST≤ 8 xULN); (ALT>8 xULN and ALT ≤ 20 xULN) or (AST>8xULN and AST≤ 20 xULN); ALT>20 xULN or AST> 20 xULN

Alkaline Phosphatase	
>ULN - ≤ 1.5xULN >1.5 – ≤ 2.5 xULN >2.5 – ≤ 5.0 x ULN >5.0 – ≤ 20.0 x ULN >20.0 x ULN

Total Bilirubin	
>ULN - ≤ 1.5 x ULN >1.5 – ≤ 2 x ULN >2 – ≤ 3 x ULN >3 – ≤ 10 x ULN

	>10 x ULN
ALT and Total Bilirubin	ALT>3xULN and TBILI>2xULN
AST and Total Bilirubin	AST>3xULN and TBILI>2xULN
(ALT or AST) and Total Bilirubin	(ALT>3xULN or AST>3xULN) and TBILI>2xULN
Hematology	
WBC	WBC decreased <LLN - $\geq 3.0 \times 10^9 /L$ <3.0 - $\geq 2.0 \times 10^9 /L$ <2.0 - $\geq 1.0 \times 10^9 /L$ <1.0 x 10e9 /L
	Leukocytosis >100 x 10e9 /L
Lymphocytes	Lymphocyte decreased <LLN - $\geq 0.8 \times 10^9 /L$ <0.8 - $\geq 0.5 \times 10^9 /L$ <0.5 - $\geq 0.2 \times 10^9 /L$ <0.2 x10e9 /L
	Lymphocyte increased >4 - $\leq 20 \times 10^9/L$ >20 x10e9/L
Neutrophils	Neutrophil decreased <LLN - $\geq 1.5 \times 10^9 /L$ <1.5 - $\geq 1.0 \times 10^9 /L$ <1.0 - $\geq 0.5 \times 10^9 /L$ <0.5 x10e9 /L
Hemoglobin	Hgb decreased (anemia) <LLN - $\geq 100 \text{ g/L}$ <100 - $\geq 80 \text{ g/L}$ < 80 g/L
	Hgb increased >ULN - $\leq 20 \text{ g/L above ULN}$ >20 g/L above ULN - $\leq 40 \text{ g/L above ULN}$ >40 g/L above ULN
Platelets	Platelet decreased <LLN - $\geq 75.0 \times 10^9 /L$ <75.0 - $\geq 50.0 \times 10^9 /L$ <50.0 - $\geq 25.0 \times 10^9 /L$ <25.0 x 10e9 /L

Statistical Analysis Plan (Methods)
Vertex Study: VX14-661-110

Note: Sources utilized for threshold analyses:

- NCI CTC-AE v4.03;
- FDA Guidance for Industry: Toxicity Grading Scale for Healthy Adult and Adolescent Volunteers Enrolled in Preventive Vaccine Clinical trials;
- FDA Guidance for Industry – DILI: Premarketing Clinical Evaluation.

Table 11-4 Threshold Criteria for Coagulation

CRITERIA for POTENTIALLY CLINICALLY SIGNIFICANT ECGs
Ref.: CPMP 1997 guideline.

Parameter	Threshold
Activated partial thromboplastin time (PTT)	>ULN - $\leq 1.5 \times$ ULN >1.5 – $\leq 2.5 \times$ ULN >2.5 x ULN
Prothrombin time (PT) International Normalized Ratio (INR)	>ULN - $\leq 1.5 \times$ ULN >1.5 – $\leq 2.5 \times$ ULN >2.5 x ULN

Note: Sources utilized for threshold analyses:

- NCI CTC-AE v4.03;
- FDA Guidance for Industry: Toxicity Grading Scale for Healthy Adult and Adolescent Volunteers Enrolled in Preventive Vaccine Clinical trials;
- FDA Guidance for Industry – DILI: Premarketing Clinical Evaluation.

Table 11-5 Threshold Criteria for ECGs

CRITERIA for POTENTIALLY CLINICALLY SIGNIFICANT ECGs	
Ref.: CPMP 1997 guideline.	
Parameter	Threshold
HR	Bradycardia
	<50 bpm
	<45 bpm
	Decrease from baseline ≥ 10 bpm
	Decrease from baseline ≥ 20 bpm
	<50 bpm and decrease from baseline ≥ 10 bpm
	<50 bpm and decrease from baseline ≥ 20 bpm
	Tachycardia
	>100 bpm
	>115 bpm
	>130 bpm
	Increase from baseline ≥ 10 bpm
	Increase from baseline ≥ 20 bpm
	>100 bpm and increase from baseline ≥ 10 bpm
>100 bpm and increase from baseline ≥ 20 bpm	
PR	≥ 240 ms
	≥ 300 ms
	≥ 200 ms and increase from baseline ≥ 40 ms
	≥ 200 ms and increase from baseline ≥ 100 ms
QRS	>110 ms
	>160 ms
	Increase from baseline ≥ 20 ms
	Increase from baseline ≥ 40 ms
QTc	>450 ms (Male)
	>470 ms (Female)
	≥ 500 ms
	Increase from baseline >10 ms
	Increase from baseline >20 ms
	Increase from baseline >40 ms
	Increase from baseline >60 ms

Note: Sources utilized for threshold analyses:
 - NCI CTC-AE v4.03;

Statistical Analysis Plan (Methods)
Vertex Study: VX14-661-110

- FDA Guidance for Industry: Toxicity Grading Scale for Healthy Adult and Adolescent Volunteers Enrolled in Preventive Vaccine Clinical trials;
- FDA Guidance for Industry – DILI: Premarketing Clinical Evaluation.

Table 11-6 Threshold Criteria for Vital Signs

CRITERIA for POTENTIALLY CLINICALLY SIGNIFICANT VITAL SIGNS	
Parameter	Threshold Criteria
HR	Same PCS as above in ECG category
SBP	
SBP increased
 
>140 mmHg >160 mmHg >10 mmHg increase from baseline >20 mmHg increase from baseline
 
>140 mmHg & >10 mmHg increase from baseline >140 mmHg & >20 mmHg increase from baseline >160 mmHg & >10 mmHg increase from baseline >160 mmHg & >20 mmHg increase from baseline
 <hr/> 
SBP decrease
 
<90 mmHg <80 mmHg >10 mmHg decrease from baseline >20 mmHg decrease from baseline
 
<90 mmHg and >10 mmHg decrease from baseline <90 mmHg and >20 mmHg decrease from baseline <80 mmHg and >10 mmHg decrease from baseline <80 mmHg and >20 mmHg decrease from baseline

DBP	
DBP increased
 
>90 mmHg >100 mmHg >5 mmHg increase from baseline >10 mmHg increase from baseline
 
>90 mmHg and >5 mmHg increase from baseline >90 mmHg and >10 mmHg increase from baseline >100 mmHg and >5 mmHg increase from baseline >100 mmHg and >10 mmHg increase from baseline

DBP decreased

<60 mmHg
<45 mmHg
>5 mmHg decrease from baseline
>10 mmHg decrease from baseline

<60 mmHg and >5 mmHg decrease from baseline
<60 mmHg and >10 mmHg decrease from baseline
<45 mmHg and >5 mmHg decrease from baseline
<45 mmHg and >10 mmHg decrease from baseline

Weight

Weight gain
≥5 % increase from baseline
≥10 % increase from baseline
≥ 20% increase from baseline

Weight loss
≥5 % decrease from baseline
≥10 % decrease from baseline
≥ 20% decrease from baseline

Note: Sources utilized for threshold analyses:

- NCI CTC-AE v4.03;
- FDA Guidance for Industry: Toxicity Grading Scale for Healthy Adult and Adolescent Volunteers Enrolled in Preventive Vaccine Clinical trials;
- FDA Guidance for Industry – DILI: Premarketing Clinical Evaluation

